5.5. Interim Analyses

An interim analysis of the Primary Endpoints will be performed after 179 subjects or more have completed their prescription wear time. This analysis will be used to stop the trial early for both safety and effectiveness.

This interim analysis will be analyzed as described in Section 5.1 above, with the exception that a one-sided upper 97% confidence bound will be used. This effectively spends 0.03 alpha on the interim analysis, reserving 0.02 alpha for the final analysis. Splitting the overall alpha into two pieces that add up to the overall alpha is a recognized way of controlling the Type I error rate. This can be seen by calculating the probability of making a Type I error. First calculate the probability of not making a Type I error which is:

Prob(no Type I in interim analysis)*Prob(no Type I in final analysis)= 0.97*0.98=0.9506

The probability of making a Type I error is then one minus the probability of not making any Type I errors which is:

Prob(Type I error)= 1.0 - 0.9506 = 0.0494

This particular split in alpha also corresponds to using a cumulative error spending function of Jennison and Turnbull (2000) defined as:

$$E(t,\rho) = \begin{cases} 1 & if \quad t \ge 1 \\ t^{\rho} & if \ 0 < t < 1 \\ 0 & otherwise \end{cases}$$

where ρ is the power parameter (here ρ =1.059) and t is the information fraction at the time of the interim analysis (here t = 179/290). Given these values, the amount of alpha spent at the interim analysis is:

 $\alpha^* E(179/290, 1.059) = 0.05^*(179/290)^{1.059} = 0.02999$

The safety endpoint will also be tested at this interim analysis only if the primary effectiveness endpoint is achieved. The trial will only be stopped if both the primary effectiveness and primary safety endpoints are achieved.

There is another planned analysis when 100 subjects have completed their prescription wear time, which will be performed to support application for CE mark. The data will be summarized descriptively and no formal hypothesis testing will be done at this point, so no adjustment for Type I error rate is necessary. Once discussions with the Notified Body are concluded, this document will be updated with details regarding the analysis.

6. Handling of Missing Data

It is expected that most subjects will wear the device between 40 and 90 days. Subjects with missing wear times will not have their data imputed for the purpose of the primary endpoint analysis.

There may be occasions when a treating physician recommends that a subject not wear the Jewel for a certain period of time for medical reasons. The duration of these periods when the subject is not wearing the Jewel at the treating physician direction will not be used in the analyses of primary, secondary, or additional endpoints. Reasons for not wearing the device may include, but are not limited to: undergoing a medical procedure (for example, MRI, CT), skin issues, resolution of adverse events that could impact device.

7. Study Subjects

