5.1. Primary Effectiveness Endpoints

All shocks during analyzable wear time will be recorded, centrally evaluated and adjudicated by the Clinical Events Committee (CEC), and reported.

The primary effectiveness endpoint is the rate of inappropriate shock. A one-sided upper 98% confidence limit will be calculated for the inappropriate shock rate per 100 patient-months at the final analysis. Specifically, an intercept-only Poisson regression model will be fit to the data. All wear times through the first inappropriate shock or through death or withdrawal or wear times for subjects without inappropriate shock, death, or withdrawal at the time of analysis will contribute to the Poisson regression model. The one-sided upper 98% confidence limit inappropriate shock rate will be calculated by taking the one-sided upper 98% confidence limit of the intercept parameter in the regression model. The null hypothesis will be rejected if the upper confidence limit on the inappropriate shock rate is less than 2.0.

The formal hypotheses are:

 H_0 : Inappropriate shock rate ≥ 2.0 per 100 patient-months H_a : Inappropriate shock rate < 2.0 per 100 patient-months

The analysis will be re-run on the per protocol analysis population if that population is different from the primary analysis population. Results of this analysis are strictly supportive.

Note that subjects experiencing an inappropriate shock will continue to be followed and accumulate wear time in order to collect data on the other endpoints of this trial.

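### SAP 5.5 states an overall effectiveness type I error of 0.0494 by treating two nested looks as independent; the additive 0.03/0.02 split is valid, but the stated figure is not the error of this design

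*SAP*

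**What the plan says.** SAP 5.5 plans one interim test of effectiveness: "An interim analysis of the Primary Endpoints will be performed after 179 subjects or more have completed their prescription wear time". At that look "a one-sided upper 97% confidence bound will be used". For the final analysis SAP 5.1 says: "A one-sided upper 98% confidence limit will be calculated for the inappropriate shock rate per 100 patient-months at the final analysis". The null hypothesis is rejected when the limit lies below 2.0 per 100 patient-months.

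SAP 5.5 then gives three accounts of why the error is controlled:

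- An additive split: "This effectively spends 0.03 alpha on the interim analysis, reserving 0.02 alpha for the final analysis", with the remark that pieces summing to the overall alpha control the error.
- A product, introduced by "This can be seen by calculating the probability of making a Type I error": "Prob(no Type I in interim analysis)*Prob(no Type I in final analysis)= 0.97*0.98=0.9506", and hence "Prob(Type I error)= 1.0 - 0.9506 = 0.0494".
- A spending function: "This particular split in alpha also corresponds to using a cumulative error spending function", of power form with ρ = 1.059, evaluated at t = 179/290 to give 0.02999 at the interim.

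This point covers the effectiveness endpoint only. The safety endpoint has its own 95% bound (SAP 5.3).

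**The concern.** Multiplying the two probabilities of no error gives the joint probability only if the two tests are independent. Here they are nested. The final analysis pools all analyzable wear time (SAP 3.1 and 5.1), so data from the 179 interim subjects are part of the 290-subject result. The SAP's own information fraction of 179/290 assumes the same accumulation. The stated 0.0494 is therefore a property of a different design.

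The spending-function sentence raises a second, smaller question. A reader who takes the correspondence to cover both looks would reconstruct a final limit other than the 98% limit that SAP 4.1 and 5.1 and Protocol 3.2.1 and 9.1 specify.

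What is at stake is the accuracy of the SAP's only demonstration of error control for an endpoint that can contribute to early stopping.

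**Working it through.** **Inputs.** Levels 0.03 and 0.02, t = 179/290 and ρ = 1.059 (SAP 5.5). Null rate 2.0 per 100 patient-months and intercept-only Poisson regression (SAP 5.1). Wear time Normal with mean 2.5 and SD 0.5 months, exponential time to first shock, 0.5 events substituted when there are none, and expected rate 0.37 per 100 (SAP 8). Interim power above 83% (Protocol 3.2.1) and final power about 98% (SAP 8).

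**1. The SAP's own figures reproduce.** 1 − 0.97 × 0.98 = 1 − 0.9506 = 0.0494. Also 0.05 × (179/290)^1.059 = 0.0300, against 0.02999 stated. The arithmetic is right; the independence step is not.

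**2. Overall error with correlated looks, normal theory.** The correlation is √(179/290) = √0.617 = 0.786. The critical values are z(0.97) = 1.881 and z(0.98) = 2.054.

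- Overall error = 1 − P(Z1 < 1.881, Z2 < 2.054) = 0.0399.
- Probability that both looks reject = 0.03 + 0.02 − 0.0399 = 0.0101. The product implies 0.03 × 0.02 = 0.0006.
- New error added by the final look = 0.0399 − 0.0300 = 0.0099, about half of the 0.02 reserved.
- At other information fractions the overall error is 0.0419 (t = 0.50), 0.0383 (t = 0.70) and 0.0361 (t = 0.80).

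**3. Overall error under the SAP's section 8 model.** The limit used is Wald on the log-rate intercept: (d/T) × exp(z/√d) for d events in T patient-months. At 0.37 per 100 this gives power 0.838 at 179 subjects (97% limit) and 0.979 at 290 (98% limit), matching the documents. Likelihood-ratio, exact and score limits give about 0.92 at the interim, so only the Wald limit comes close to the stated interim power.

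At 2.0 per 100, with 200,000 simulated trials: interim 0.0140, final 0.0116, either look 0.0214. An independent run gave 0.0137, 0.0114 and 0.0210. The product of the simulated single-look values is 1 − 0.9860 × 0.9884 = 0.0254. Dependence therefore takes 0.0254 to 0.0214; the rest of the gap from 0.0494 is the conservatism of the limit with few events.

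**4. Fixed exposure.** T = 179 × 2.5 = 447.5 and 290 × 2.5 = 725 patient-months, so the null means are 8.95 and 14.5.

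| Look | Events | Wald upper limit per 100 | Below 2.0? |
|---|---|---|---|
| Interim, 97% | 3 | 1.99 | yes |
| Interim, 97% | 4 | 2.29 | no |
| Final, 98% | 6 | 1.91 | yes |
| Final, 98% | 7 | 2.10 | no |

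P(X ≤ 3 | 8.95) = 0.0220. The final look adds 0.0049, for a total of 0.0269. This sits near an edge: three interim events pass only above about 444.3 patient-months. With other mean wear times the fixed-exposure Wald error is 0.014 at 2.0 months, 0.023 at 3.0 and 0.032 near 2.87.

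**5. Final boundary of the spending function.** Spending a cumulative 0.05 by t = 1, after 0.0300 at the interim, needs a nominal final level of 0.0341 (z = 1.824), that is, a limit of about 96.6%. At 725 patient-months seven shocks would then pass (upper limit 1.92), against six under the 98% limit.

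**6. Does the bound depend on the limit type?** Yes. Under a likelihood-ratio limit the single looks can exceed 0.03 or 0.02. At fixed exposure the overall error is then 0.052 at 2.25 and at 3.0 months mean wear, and 0.077 near 1.67 months.

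**The case against.** The strongest defence is that nothing operational is wrong. The valid argument, that the pieces sum to the overall alpha, already stands in SAP 5.5. Under the Wald limit that the stated power implies, 0.0494 errs on the safe side. The SAP also claims only that the split corresponds to the spending function, and the one amount it computes is correct. All of this stands, and it sets the severity. It does not rescue the 0.0494, which is stated as the error probability and not as a bound.

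Two limits on the replacement figures also stand. The 0.021 and 0.027 belong to a Wald limit at 2.5 months mean wear and are not a general range. The 0.040 assumes t = 179/290, whereas SAP 5.1 also counts wear of subjects still free of shock, death or withdrawal at the analysis, so t may be larger.

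A reader might infer more than the documents support:

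- *That the error is inflated.* The additive bound needs no independence, and the Wald results lie well below 0.05.
- *That the 98% limit is wrong because it is not the spending function's boundary.* The SAP does not say that it derived the final limit from the function, and the documents state the 98% limit consistently.
- *That an interim after more than 179 subjects overspends.* The function would allow 0.0343 at 203 subjects (t = 0.70) and 0.0395 at 232 (t = 0.80), both above the fixed 0.03. Only the stated match at 179/290 lapses.

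**Conclusion.** The point holds as a low-severity correction of a stated figure. The 0.0494 requires independent looks and is not the overall effectiveness error of this design. With nominal levels held it is about 0.040 by normal theory at t = 179/290. Under the SAP's section 8 model with a Wald limit and 2.5 months mean wear it is about 0.021, or 0.027 at fixed exposure.

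The spending-function sentence is right for the interim amount only; the function's final level would be 0.034 and not 0.02. The 0.03/0.02 split remains valid. Its bound of 0.05 is conditional on each limit holding its nominal level, which the SAP cannot guarantee while it leaves the limit type unnamed. No limit, sample size or decision rule needs to change.

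**What to change.** In SAP 5.5:

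1. Keep the sentence that the pieces add up to the overall alpha.
2. Delete the product calculation and the 0.0494. Write instead, for example: *For the primary effectiveness endpoint, one-sided alpha is split 0.03 (interim, 97% limit) and 0.02 (final, 98% limit). Because interim subjects enter the final analysis, the tests are correlated; by Bonferroni the overall error for this endpoint is at most 0.05, provided each limit holds its nominal level.*
3. Name the limit type. A Wald limit on the log-rate intercept is the one that reproduces the stated interim power.
4. Delete the spending-function paragraph, or say that it describes only the amount spent at an interim at t = 179/290 and does not define the final limit.
5. If a numerical error is quoted, give its method and its wear-time assumption.

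The cost is an edit to two paragraphs of one SAP section. No subjects are added, and the protocol text and both confidence limits stay as they are.

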3.2 Endpoints

3.2.1 Primary Effectiveness Endpoint

To demonstrate an observed inappropriate shock rate of no more than 2.0 inappropriate shocks per 100 patient-months using a one-sided upper 97% confidence interval and >83% power at the interim analysis; and a 98% confidence interval and >98% power for the final analysis.

An inappropriate shock is defined as a shock delivered during a period where the study subject is not experiencing life threatening VT or VF. Only first inappropriate shocks will contribute the analysis of this endpoint. All inappropriate shocks will be reviewed and adjudicated by a Clinical Events Committee (CEC) and reported throughout the prescription period.

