9.1 Statistical Hypotheses

Primary Effectiveness Endpoint:

The primary effectiveness endpoint is the rate of inappropriate shock. A one-sided upper 98% confidence limit will be calculated for the inappropriate shock rate per 100 patient-months at the final analysis.

Only first inappropriate shocks will contribute the analysis of this endpoint. All wear times through the first inappropriate shock or through death or withdrawal will contribute to the Poisson regression model. All follow-up beyond the first inappropriate shock will not be used.

The formal hypotheses are:

H0: Inappropriate shock rate \geq 2.0 per 100 patient-months

Ha: Inappropriate shock rate < 2.0 per 100 patient-months.

Primary Safety Endpoint:

The primary safety endpoint is the rate of subjects experiencing a clinically significant ADE. The primary safety endpoint will use a one-sided, exact 95% upper confidence bound which will be compared to the performance goal of 15%. The hypotheses tested will be as follows:

H0: π ≥ 0.15 Ha: π < 0.15

where π is the observed proportion of subjects experiencing a clinically significant cutaneous adverse device event.

Secondary Endpoint:

The secondary endpoint of successful conversion of at least one shockable rhythm with a salvo of up to five (5) shocks will not be formally tested.

The secondary endpoints of compliance rate of subjects wearing the Jewel, and the QOL analysis will not be formally tested.

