9.4 Statistical Analyses

9.4.1 General Approach

Descriptive statistics for continuous variables will include the mean, standard deviation, N, median, and range in the form of a minimum and maximum. Categorical data will be summarized using percentages and the count (numerator) and N (denominator) used to calculate the percentage. All formal testing will be done at the 0.05 level of significance unless otherwise stated.

The details of the statistical analysis can be found in the JEWEL SAP.

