9.4.4 Planned Interim Analyses

A single interim analysis will be performed after 179 or more subjects have completed their prescription wear time. This analysis will be used to stop the trial early for both safety and effectiveness. The Type I error rate for this analysis will be set to 0.03.

There is another planned analysis once 100 subjects have completed their prescription wear time, which will be performed to support application for CE mark. The data will be summarized descriptively and no formal hypothesis testing will be done at this point, so no adjustment for the Type I error rate is necessary. The results of the 100 subject interim analysis will not be used to terminate the IDE trial prior to completion of enrollment and subject follow up.

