5.3. Primary Safety Endpoints

The statistical method used for testing the primary safety endpoint will use a one-sided, exact 95% upper confidence bound which will be compared to the performance goal of 15%. The exact confidence bound will be constructed using the Clopper-Pearson method. The hypotheses tested will be as follows:

 $H_0: \pi \ge 0.15 \\ H_a: \pi < 0.15$

where π is the observed proportion of subjects experiencing a clinically significant cutaneous adverse device event.

An ADE will be considered "clinically significant" if it results in the subject being permanently withdrawn from the clinical trial by the Investigator.

Additionally, all Adverse Device Effects and device-related Serious Adverse Events (SAE) will be tabulated and presented along with duration and severity. The proportion of subjects experiencing an ADE or SAE will also be presented. All device-related events will be reviewed by the Oversight Committee. All Adverse Device Effects and device-related SAEs will be tabulated and presented.

A summary of all AEs and SAEs, including the proportion of subjects experiencing an AE or SAE, along with duration, severity, and relatedness to the Jewel will also be presented to ensure that device safety performance is adequately summarized.

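### The primary safety endpoint can be tested at two looks, but no safety confidence level is given for each look, and the only stated bound (95%) does not hold 5% over both

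*SAP*

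**What the plan says.** **Two looks at safety.** SAP 5.5 plans the interim for both primary endpoints: "An interim analysis of the Primary Endpoints will be performed after 179 subjects or more have completed their prescription wear time". It then adds: "The safety endpoint will also be tested at this interim analysis only if the primary effectiveness endpoint is achieved". Stopping requires both endpoints to pass. If effectiveness passes and safety does not, the trial continues and safety is tested again at the final analysis.

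**The stated safety bound.** SAP 5.3 says that the safety test "will use a one-sided, exact 95% upper confidence bound which will be compared to the performance goal of 15" percent, built by the Clopper-Pearson method. Protocol 9.1 agrees: "The primary safety endpoint will use a one-sided, exact 95% upper confidence bound". Neither sentence names a look. Protocol 3.2.2, the safety endpoint section, gives no confidence level. Protocol 9.4.1 supplies a default: "All formal testing will be done at the 0.05 level of significance unless otherwise stated".

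**The split levels.** Protocol 3.2.1, under effectiveness, gives a "97% confidence interval and >83% power at the interim analysis; and a 98% confidence interval and >98% power for the final analysis". SAP 5.5 says that the interim will be "analyzed as described in Section 5.1 above, with the exception that a one-sided upper 97% confidence bound will be used", and Section 5.1 is the shock-rate analysis. The SAP then describes 0.03 as spent at the interim and 0.02 as kept for the final. Protocol 9.4.4 says: "The Type I error rate for this analysis will be set to 0.03". The sentence just before that one describes the interim as a basis for stopping early on both safety and effectiveness.

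**The concern.** For effectiveness, the SAP splits the error between two looks and argues that the total stays below 5%. For safety, which is also a primary endpoint and a condition for stopping early, there is no equivalent statement. If the one documented safety bound is applied each time safety is tested, a device whose true rate sits at the 15% limit has two chances to pass.

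The text allows more than one pair of levels, and the pairs give different cut-offs. Eighteen events in 179 subjects pass at 95% and fail at 97%. A final count of 31 to 33 events in 290 passes at 95% and fails at 98%. If the level is settled after interim data are seen, the result on a primary endpoint could depend on that choice.

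**Working it through.** **Inputs.** Performance goal 15%, one-sided Clopper-Pearson bound (SAP 5.3). Looks at 179 and 290 subjects (Protocol 4.1). Effectiveness power at the interim above 83% (Protocol 3.2.1).

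**The plan's own figures.**
- 1 − 0.97 × 0.98 = 0.0494, as in SAP 5.5.
- 0.05 × (179/290)^1.059 = 0.0300, matching the stated 0.02999 to rounding.
- Simulating effectiveness under SAP section 8 assumptions (rate 0.37 per 100 months, wear mean 2.5 and SD 0.5 months) gives power of 98.1% at 290 (stated: about 98%) and 83.8% at 179 (stated: >83%).

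No two-look figure is stated for safety.

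**Step 1: cut-offs.** The largest count x with Beta⁻¹(1 − α; x + 1, n − x) < 0.15:

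| Bound | n = 179 | n = 290 |
|---|---|---|
| 95% | 18 | 33 |
| 96.6% | – | 32 |
| 97% | 17 | – |
| 98% | 16 | 30 |
| 99% | 15 | – |

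**Step 2: two-look error at a true 15%.** Let X₁ be the interim count and Y the count in the 111 subjects added afterwards. Then

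P(pass) = P(X₁ ≤ c₁) + Σ over x > c₁ of P(X₁ = x) · P(Y ≤ c₂ − x).

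| Levels (interim/final) | Pass at interim | Pass only at final | Total |
|---|---|---|---|
| 95%/95% | 3.53% | 2.82% | 6.35% |
| 97%/95% | 2.06% | 3.40% | 5.45% |
| 97%/98% | 2.06% | 0.70% | 2.75% |

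(Parts may not add exactly because of rounding.) A single safety test at the final, at 95%, has error 4.63%.

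**Step 3: the effectiveness condition.** Safety is tested at the interim only if effectiveness passes. Take that probability as 0.84 (the simulated value, rounded) and independent of safety events:
- 95%/95%: 0.84 × 6.35 + 0.16 × 4.63 = 6.07%.
- 97%/95%: 0.84 × 5.45 + 0.16 × 4.63 = 5.32%.

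**Step 4: away from the boundary.** With 95%/95% and the condition always met, a true 16% passes 2.6% of the time and a true 17% passes 0.95%.

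**Step 5: other sizes.** The interim is at 179 or more, and the safety population (SAP 3.3) can differ from the analyzable count. Over an assumed grid of interim 179–224 and final 290–370 (3,726 pairs, condition always met), 95%/95% gives 5.1–7.8%, 97%/95% gives 4.2–6.5% (above 5% in 72% of pairs), and 97%/98% gives 2.4–4.1%. The grid is an assumption; it shows only that the answer depends on the sizes.

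**The case against.** The strongest reply is that the 0.03/0.02 split already covers safety. SAP 5.5 opens with both primary endpoints and assigns the alpha to analyses. Protocol 9.4.4 names safety in the sentence before the 0.03, and the 0.05 default in Protocol 9.4.1 gives way where something else is stated. This has force for the interim: 97% for safety at that look is at least as tenable as 95%. It does not carry through to the final. No passage attaches 98% to safety, both safety sections state 95%, and with 97% then 95% the error is still 5.45% (5.3% with the effectiveness condition at 0.84).

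A reader might infer that the plan commits to 95% at both looks, so that its safety error is 6.35%. The documents do not support that as a settled fact. It is one tenable reading, and 6.35% also needs effectiveness to be certain to pass at the interim. A reader might equally infer a fault in the effectiveness alpha split; nothing here bears on it.

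Two further defences fail. Making the interim safety test conditional on effectiveness orders the endpoints but does not adjust for testing safety twice. Requiring both endpoints to pass removes the need to adjust across endpoints, not across repeated looks at one of them.

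It is fair to say that the excess is small and confined to true rates close to 15%.

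**Conclusion.** The point holds as a gap in the specification with a modest multiplicity consequence. The only stated safety bound, used at both looks, does not hold 5%. At 179/290 and a true 15%, the error runs from 2.75% to 6.35% depending on the reading, so the excess over 5% runs from none to 1.35 percentage points. The two readings that keep the documented 95% bound at the final both exceed 5% at these sizes. The one that does not relies on a 98% safety bound that appears nowhere.

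The figures rest on exact binomial counts at 179 and 290. The figures that allow for the effectiveness condition assume that it is met with probability 0.84, independently of safety. This should be fixed before the interim; it does not undermine the design.

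**What to change.** Before interim data are seen:
1. State the safety confidence level at each look in SAP 5.3 and 5.5 and in Protocol 9.1.
2. Say in Protocol 9.4.4 whether the 0.03 covers safety.
3. Choose a pair whose exact two-look error is at most 5%. Recheck it at the actual safety population sizes, lowering the final cut-off if needed.
4. Say that safety is tested once, at the final, if effectiveness is not met at the interim.

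The choice of pair is a trade-off for the sponsor. The documents give no expected safety rate, so true rates of 8% and 10% are assumed below. All entries are for 179/290 with the effectiveness condition met.

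| Levels | Error at 15% | Passes safety at interim, true 8% | Overall safety power, true 10% |
|---|---|---|---|
| 95%/95% (for comparison) | 6.35% | 87.3% | 83.0% |
| 98%/95% | 4.99% | 73.4% | 81.7% |
| 99%/95% | 4.8% | 64.0% | 81.4% |
| 97%/96.6% | 4.2% | 81.2% | 77.5% |
| 97%/98% | 2.75% | 81.2% | 67.2% |

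The 98%/95% pair has a thin margin: on the assumed grid it exceeds 5% in 1,393 of 3,726 size pairs, against 476 for 99%/95%. The 97%/98% pair never exceeds 5% there, but costs the most power.

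The cost is wording in four sections, a somewhat lower chance of stopping early (hence higher expected enrolment) and some safety power. The maximum sample size, data collection and effectiveness bounds stay as they are.
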